MK-6482 Administration			X				To be administered immediately following the Friday or Saturday scheduled HD session.  There will be a washout period of at least 7 days between study intervention administrations in each period.
Pharmacokinetics							
Blood for Plasma MK-6482 Assay			X	X	X	X	To be collected at predose and at 0.5, 1, 1.5, 2, 3, 4, 5, 6, 9, 12, 24, 36, 48, and 72 hours postdose.
Blood for Protein Binding			X				To be collected at predose.
Biomarkers							
Blood for Genetic Analysis			X				To be collected predose from enrolled participants only [Sec. 8.8] .
Abbreviations: AE=adverse event, BMI=body mass index, BP=blood pressure, C-I=check-in, Chem=chemistry, CYP=cytochrome P450, ECG=electrocardiogram, EM=extensive metabolizer, ESRD=end stage renal disease, FBR=future biomedical research, FSH=follicle-stimulating hormone, HD=hemodialysis, Hem=hematology, HIV=human immunodeficiency virus, HR=heart rate, IM=intermediate metabolizer, RR=respiratory rate, SAE=serious adverse event(s), T=body temperature, UA=urinalysis, UGT=uridine 5'-diphospho-glucuronosyltransferase.							

Period 2 for ESRD Group						
Study Period:	Intervention				Poststudy or ET	Notes
Scheduled Day	-1 (C-I)	1	2	3	4	
Administrative Procedures						
Prior/Concomitant Medication Review	X	X	X	X	X	Sec. 6.5
Domiciling	X	X	X	X	X	Sec. 8.1.12
Safety Procedures						
Complete Physical Examination					X	To be conducted also for participants who discontinue/withdraw from the study.
Symptom Driven Physical Examination	X	X	X	X	X	Only to be conducted if the participant's symptoms warrant an examination or at the investigator's discretion.
Weight					X	
HR, BP, and RR	X	X	X	X	X	To be performed at Day -1, predose, at 24, 48, and 72 hours postdose, and poststudy or prior to early termination from the study.
T	X	X	X	X	X	To be performed at Day -1, predose, at 24, 48, and 72 hours postdose, and poststudy or prior to early termination from the study. To be also performed at poststudy.
12-lead ECG	X		X		X	To be performed at Day -1, at 24 and 72 hours postdose, and poststudy or prior to early termination from the study.
Pulse Oximetry	X	X	X	X	X	To be performed at Day -1, predose, at 24, 48, and 72 hours postdose, and poststudy or prior to early termination from the study.
Hem, Serum Chem, and UA	X		X		X	To be performed at Day -1, at 24 and 72 hours postdose, and poststudy or prior to early termination from the study.

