In Period 2, ESRD participants will receive a single oral dose of 120 mg MK-6482 approximately 2 hours prior to their normally scheduled HD followed by 72 hours blood sampling for PK assessment of MK-6482. For participants following a Monday, Wednesday, Friday HD schedule, MK-6482 will be administered approximately 2 hours prior to their Friday HD session. For participants following a Tuesday, Thursday, Saturday HD schedule, MK-6482 will be administered approximately 2 hours prior to their Saturday HD session. The 4-hour HD session should initiate immediately following the 2-hour PK blood draw. A pre-dialyzer plasma sample will be collected at the start of HD. During this dialysis session, pre- and post-dialyzer plasma samples will be collected approximately every 30 minutes during HD for MK-6482 analysis.

Healthy matched control participants will receive a single oral dose of 120 mg MK-6482, followed by 72 hours of blood sampling for PK assessment of MK-6482.

Safety will be monitored throughout the study.

Because this is a Phase 1 assessment of MK-6482 in humans, the PK, pharmacodynamic, and safety profiles of the compound are still being elucidated. This protocol is therefore written with flexibility to accommodate the inherent dynamic nature of Phase 1 clinical studies. Refer to [Section 8.11.6](#) for examples of modifications permitted within the protocol parameters.

Specific procedures to be performed during the study, including prescribed times and associated visit windows, are outlined in [Section 1.3](#) of the SoA. Details of each procedure are provided in [Section 8](#).

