#### Male Participants

5. Male participants are eligible to participate if they have been vasectomized or undergone surgical sterilization for at least 4 months or more prior to study intervention administration and agree to the following during the intervention period and for at least 7 days (time needed for MK-6482 to be eliminated) after administration of study intervention:
  - Be abstinent from heterosexual intercourse as their preferred and usual lifestyle (abstinent on a long-term and persistent basis) and agree to remain abstinent  
OR
  - Must agree to use contraception as detailed below:
    - Agree to use a male condom plus partner use of an additional contraceptive method when having penile-vaginal intercourse with a WOCBP who is not currently pregnant. Note: Men with a pregnant or breastfeeding partner must agree to remain abstinent from penile-vaginal intercourse or use a male condom during each episode of penile-vaginal penetration.

Contraceptive use by men should be consistent with local regulations regarding the methods of contraception for those participating in clinical studies.

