### **9.1 Statistical Analysis Plan Summary**

This section contains a brief summary of the statistical analyses for this study. Full detail is in the SAP to be provided separately.

Detailed methodology for summary and statistical analyses of the data collected in this study will be documented in an SAP. The SAP will be prepared by Celerion and agreed upon with the Sponsor. This document may modify the plans outlined in the protocol; however, any major modifications of the primary endpoints definition and/or its analysis will also be reflected in a protocol amendment. Additional statistical analyses other than those described in this section may be performed if deemed appropriate.

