## 9.4 Analysis Endpoints

The primary PK endpoints will be AUC0-inf and Cmax of MK-6482 following a single oral dose of MK-6482 to participants with ESRD before and after HD to each other and to those in healthy matched control participants.

Additional PK endpoints will include AUC0-last, AUC0-24, AUC%extrap, Cmax, C24, Tmax, apparent terminal  $t_{1/2}$ ,  $\lambda_z$ , CL/F, and Vz/F.

For ESRD participants in Period 2, the secondary PK endpoint for plasma MK-6482 will include CLDplasma. Additional PK endpoints for ESRD participants in Period 2 will include Ca, Cv, AUC(2-6)Ca, and AUC(2-6)Cv.

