Figures showing summary plasma concentration-time profiles by population for MK-6482 (linear plot with arithmetic mean ( $\pm$ SD) for concentration and semi-log plot with arithmetic mean) will be provided. A table showing summary PK parameter values with GMs (%GCV) by population, will be provided for MK-6482 AUC0-inf, AUC0-24, Cmax, Tmax, and apparent terminal  $t_{1/2}$ . A table showing the GMR (ESRD before HD /normal renal function, ESRD after HD/normal renal function, ESRD before HD/ESRD after HD) and corresponding 90% CI will be provided for PK parameters, AUC0-inf and Cmax.

Individual values will be listed for each PK parameter for MK-6482 (AUC0-inf, AUC0-last, AUC0-24, AUC%extrap ([percentage of AUC0-inf obtained by extrapolation from 24 hours to  $\infty$ ]),  $\lambda_z$  [terminal elimination rate constant], Cmax, Tmax, CL/F, Vz/F,  $\lambda_z$ , apparent terminal  $t_{1/2}$ , CLD, plasma [dialysis clearance based on plasma], Ca [concentration in plasma samples from the pre-dialyzer line during the dialysis period], and Cv [concentration in plasma samples from the post-dialyzer line during the dialysis period]. The following (non-model-based) descriptive statistics will be provided: N (number of participants with

non-missing data), arithmetic mean, standard deviation, arithmetic percent CV (calculated as 100 x standard deviation/ arithmetic mean), median, minimum, maximum, geometric mean, and geometric percent CV (calculated as 100 x sqrt(exp(s) - 1), where s is the observed variance on the natural log-scale). Descriptive statistics may be provided based on UGT2B17 and/or CYP2C19 phenotypes separately.

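### AUC%extrap is defined as extrapolation from 24 h although every group is sampled to 72 h, so measured area would be reported as extrapolated (minor)

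*Combined protocol and SAP*

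**What the plan says.** In the list of individual PK parameters, Section 9.6.3 explains AUC%extrap as the "percentage of AUC0-inf obtained by extrapolation from 24 hours to" infinity. This is the only definition in the documents. Section 9.4 names the term without defining it, and Appendix 10 (Abbreviations) does not include it.

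The sampling plan runs well past 24 h. The Schedule of Activities (Sections 1.3.1 and 1.3.2) sets the same plasma times for ESRD Period 1, ESRD Period 2 and the healthy controls: "To be collected at predose and at 0.5, 1, 1.5, 2, 3, 4, 5, 6, 9, 12, 24, 36, 48, and 72 hours postdose". Section 4.1 agrees, with 72 h of sampling in ESRD Period 1 and in the controls ("followed by 72 hours of blood sampling for PK assessment of MK-6482") and in ESRD Period 2 ("followed by 72 hours blood sampling for PK assessment of MK-6482"). The one exception, also in Section 4.1, is that in Period 1 the next dialysis may have to start before 72 h, in which case a sample is taken first.

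Section 9.4 treats AUC to the last sample and AUC to 24 h as different quantities: "Additional PK endpoints will include AUC0-last, AUC0-24, AUC%extrap, Cmax, C24, Tmax". Section 9.6.3 lists both for each participant, together with AUC0-inf.

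Section 9.1 calls Section 9 a summary and refers to a separate SAP for full detail: "This document may modify the plans outlined in the protocol".

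**The concern.** AUC%extrap tells the reader how much of AUC0-inf rests on the fitted terminal slope and not on measured concentrations. It therefore has to start where measurement stops. Starting it at 24 h puts up to 48 h of observed profile, covering three planned samples, into the extrapolated part.

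AUC0-inf is a primary endpoint. A reader who finds a large AUC%extrap in the listing would conclude that AUC0-inf is poorly supported by data, when most of the supposedly extrapolated area may have been measured. The overstatement also depends on half-life. If half-life differs between ESRD participants and controls, the figure would misstate the quality of AUC0-inf by different amounts in the groups being compared.

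**Working it through.** The plan gives no AUC%extrap value to reproduce, so the check is of the definition, followed by an illustration of size.

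**Step 1: what the wording computes.**
- As written: AUC beyond 24 h as a share of AUC0-inf, that is 100 × (AUC0-inf − AUC0-24)/AUC0-inf.
- From the last quantifiable sample: 100 × (AUC0-inf − AUC0-last)/AUC0-inf.
- Difference: 100 × (AUC0-last − AUC0-24)/AUC0-inf. This is the measured area after 24 h. It is positive whenever any concentration after 24 h is quantifiable, so the direction does not depend on a PK model.

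**Step 2: inputs for the size.**
- Last planned sample 72 h (Sections 1.3.1, 1.3.2 and 4.1).
- Half-life: not given in the documents. The only related figure is in the contraception criteria, "7 days (time needed for MK-6482 to be eliminated". If 7 days is read as five half-lives (an assumption), the half-life is 168/5 = 33.6 h. The values 6, 10 and 20 h are assumptions with no source in the documents.

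**Step 3: single exponential.** The share of area beyond time T is exp(−ln2 × T/t½).

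| Assumed t½ | As written (beyond 24 h) | Beyond 72 h | Overstatement |
|---|---|---|---|
| 6 h | 6.25% | 0.02% | 6.2 points |
| 10 h | 18.95% | 0.68% | 18.3 points |
| 20 h | 43.53% | 8.25% | 35.3 points |
| 33.6 h | 60.95% | 22.64% | 38.3 points |

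If x is the share beyond 24 h, the share beyond 72 h is x³. The gap x − x³ is largest at x = 1/√3, where it is 0.385 (half-life 30.3 h). So 38.5 points is the ceiling under this model only.

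**Step 4: oral profile at the protocol's sampling times.** One-compartment oral model, linear-up log-down AUC, terminal slope fitted from 24 h to the last sample, assumed absorption rate 0.5 to 1.5 per h, last sample 72 h.

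| Assumed t½ | As written | From last sample | Overstatement |
|---|---|---|---|
| 10 h | 19.9–22.1% | 0.7–0.8% | 19–21 points |
| 20 h | 44.6–46.8% | 8.5–8.9% | 36–38 points |
| 33.6 h | 61.8–63.6% | 23.0–23.6% | 39–40 points |

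Absorption moves area to later times, so these gaps slightly exceed the single-exponential ones. At 30.3 h with the slowest absorption the gap is 40.4 points.

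**Step 5: earlier last sample.** If the last sample is at 48 h, the oral-profile overstatement is about 25–27 points at 20 h and 24–25 points at 33.6 h. It is smaller than with a 72 h sample but in the same direction.

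**The case against.** The strongest case on the other side is that nothing of consequence changes. AUC%extrap is not in the objectives table, is not modelled, and appears in neither the geometric mean table nor the ratio table. No acceptance threshold or exclusion rule depends on it, and a reader can recompute the correct share from AUC0-inf and AUC0-last in the same listing. All of this stands, and it is why the point is minor.

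It can also be said that the phrase is a drafting slip. It sits in a parenthetical list that names the terminal rate constant twice, and area measured at 36 to 72 h is by definition not obtained by extrapolation, so the wording contradicts itself more than it instructs. That is a fair description of how it may have arisen. It does not help a programmer who must turn the text into a formula: 24 h is the only starting point given.

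The separate SAP may define the term correctly. It was not available, so whether the wording reaches any output is unknown. Until that is confirmed, Section 9.6.3 holds the only definition. If the SAP or the PK software starts from the last sample, the outputs will disagree with the protocol.

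Finally, the sizes rest on assumed half-lives, and an early dialysis in Period 1 would shorten the sampled interval. Both points are correct. They affect the size and not the direction.

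**Conclusion.** The concern holds, as a minor definition error. Section 9.6.3 as worded counts measured area as extrapolated, and the resulting AUC%extrap is too high for any profile quantifiable after 24 h. That conclusion needs no PK assumption.

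The amount is illustrative: from about 6 percentage points at an assumed half-life of 6 h to about 40 points at half-lives near 30 h, given a 72 h last sample and a one-compartment profile. The consequence is limited to the listed and summarised AUC%extrap values, and arises only if the wording is carried into the SAP. No primary estimate or interval is affected.

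**What to change.** In Section 9.6.3, define AUC%extrap as 100 × (AUC0-inf − AUC0-last)/AUC0-inf, that is, extrapolation from the last quantifiable sample to infinity. Use the same definition in the separate SAP. Anchor it to the last quantifiable sample and not to a fixed 72 h, so that it also covers Period 1 profiles cut short by an early dialysis and profiles that fall below quantification sooner. If the share of exposure after 24 h is wanted in its own right, report it under another name; it already follows from AUC0-24 and AUC0-inf.

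The cost is one phrase in the protocol and the SAP, with no extra data, sampling or analysis.

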Coagulation					X	To be performed also for participants who discontinue/withdraw from the study.
Urine/Saliva Drug Screen	X					
Urine/Blood/Breathalyzer Alcohol Screen	X					
AE/SAE Review	X	X	X	X	X	See Sec. 8.11.4 for poststudy contact details.

Period 2 for ESRD Group							
Study Period:	Intervention					Poststudy or ET	Notes
Scheduled Day	-1 (C-I)	1	2	3	4		
Study Intervention Administration							
MK-6482 Administration		X					To be administered approximately 2 hours prior to the Friday or Saturday scheduled HD session.  There will be a washout period of at least 7 days between study intervention administrations in each period.
HD		X					The 4-hour HD session will be initiated immediately following the 2-hour PK blood draw.
Pharmacokinetics							
Blood for Plasma MK-6482		X	X	X	X		To be collected at predose and at 0.5, 1, 1.5, 2, 3, 4, 5, 6, 9, 12, 24, 36, 48, and 72 hours postdose.
Dialyzer Samples for Plasma MK-6482		X					A pre-dialyzer plasma sample to be collected at the start of HD. Pre-dialyzer and post-dialyzer plasma samples to be collected at 0.5, 1, 1.5, 2, 2.5, 3, 3.5, and 4 hours (immediately before HD completion) from the start of HD.
Abbreviations: AE=adverse event; BP=blood pressure, C-I=check-in, Chem=chemistry, ECG=electrocardiogram, ESRD=end stage renal disease, ET=early termination, HD=hemodialysis, Hem=hematology, HR=heart rate, PK=pharmacokinetic, RR=respiratory rate, SAE=serious adverse event(s), T=body temperature, UA=urinalysis.							

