#### **8.11.6 Study Design/Dosing/Procedures Modifications Permitted Within Protocol Parameters**

This is a Phase 1 assessment of MK-6482 in humans, and the PK, pharmacodynamic, and safety profiles of the compound are still being elucidated. This protocol is written with some flexibility to accommodate the inherent dynamic nature of Phase 1 clinical studies.

Modifications to clinical or laboratory procedures currently outlined may be required to achieve the scientific goals of the study objectives and/or to ensure appropriate safety monitoring of the study participants.

- Instructions to take study intervention with or without food or drink may also be modified based on newly available data
- Modification of the PK/pharmacodynamic sample processing and shipping details based on newly available data

The PK sampling scheme currently outlined in the protocol may be modified during the study based on newly available PK data (eg, to obtain data closer to the time of peak plasma concentrations). If indicated, these collected samples may also be assayed in an exploratory manner for metabolites and/or pharmacodynamic markers.

Up to an additional 50 mL of blood may be drawn for safety and/or PK analyses. The total blood volume withdrawn from any single participant will not exceed the maximum allowable volume during their participation in the entire study ([Appendix 8](#)).

The timing of procedures for assessment of safety procedures (eg, vital signs, ECG, safety laboratory tests, pulse oximetry, etc) may be modified during the study based on newly available data. Additional safety laboratory tests may be added to blood samples previously

drawn to obtain additional safety information. These changes will not increase the number of study procedures for a given participant during their participation in the entire study.

It is understood that the current study may use some or none of the alterations described above. Any alteration made to this protocol to meet the study objectives must be detailed by the Sponsor in a letter to the Study File and forwarded to the investigator for retention. The letter may be forwarded to the IRB/IEC at the discretion of the investigator.

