Individual participant PK parameter values will also be plotted against BSA normalized eGFR and against BSA un-normalized eGFR, using different symbols to identify participants from each population. For this analysis, eGFR may be calculated as the mean of the two values determined at the prestudy (screening) visit. Plots of PK parameters versus CLcr obtained from C-G equation may be provided. Additionally, plots of PK parameter values versus age and BMI may be provided. PK concentration listings for MK-6482 in plasma, including Ca and Cv concentrations, will be provided for each participant; AUC(2-6)Ca (plasma AUC values determined from Ca versus time profile during the dialysis period from 2 hours to 6 hours postdose using 'linear up, log down' calculation method option in WinNonlin), AUC(2-6)Cv (plasma AUC values determined from Cv versus time profile during the dialysis period from 2 hours to 6 hours postdose using 'linear up, log down' calculation method option in WinNonlin) for MK-6482 during HD in Period 2 will be provided for each ESRD participant.

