## 10.8 Appendix 8: Blood Volume Table

ESRD Participants Only	Prestudy	Treatment Periods	Poststudy	Total Collections	mL Per Collection	Total mL/Test
Safety Clinical Laboratory Tests (including hematology, serum chemistry, FSH [if scheduled at the same time])	1	6 b	1	8	12.5	100
Coagulation	1	--	1	2	3.5	7
Blood for Planned Genetic Analysis	--	1	--	1	8.5	8.5
Blood for MK-6482	--	30	--	30	4	120
Blood for Protein Binding	--	1	--	1	4	4
Pre- and Post-dialyzer Plasma for MK-6482	--	17 c	--	17	4	68
Blood for UGT2B17 Genotyping	1	--	--	1	3	3
Blood for CYP2C19 Genotyping	1	--	--	1	3	3
Total Blood Volume per Participant a						313.5 mL

a If additional PK and/or safety analysis is necessary, additional blood (up to 50 mL) may be obtained.

b If the CRU decides to confine the participants throughout the study (ie, washout period), some clinical laboratory assessments at the second check-in may not be performed at the investigator's discretion.

c Dialyzer samples collected in Period 2 only.

Healthy Participants Only	Prestudy	Treatment Period	Poststudy	Total Collections	mL Per Collection	Total mL/Test
Safety Clinical Laboratory Tests (including hematology, serum chemistry, FSH [if scheduled at the same time])	1	3	1	5	12.5	62.5
Coagulation	1	--	1	2	3.5	7
Blood for Planned Genetic Analysis	--	1	--	1	8.5	8.5
Blood for MK-6482	--	15	--	15	4	60
Blood for Protein Binding	--	1	--	1	4	4
Blood for UGT2B17 Genotyping	1	--	--	1	3	3
Blood for CYP2C19 Genotyping	1	--	--	1	3	3
Total Blood Volume per Participant a						148 mL

a If additional PK and/or safety analysis is necessary, additional blood (up to 50 mL) may be obtained.

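### Does AUC(2-6)Cv need redefining because the first post-dialyzer sample falls at about 2.5 h, not 2 h, postdose?

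*Combined protocol and SAP*

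**What the plan says.** Section 9.6.3 gives two areas for the Period 2 dialysis session, one from the pre-dialyzer line (Ca) and one from the post-dialyzer line (Cv). Both run from 2 to 6 h postdose by the linear-up, log-down rule; the second reads "AUC(2-6)Cv (plasma AUC values determined from Cv versus time profile during the dialysis period from 2 hours to 6 hours postdose".

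The Period 2 schedule in Section 1.3.1 starts the 4-hour session straight after the 2-hour PK draw. For the start it says "A pre-dialyzer plasma sample to be collected at the start of HD", and for the rest "Pre-dialyzer and post-dialyzer plasma samples to be collected at 0.5, 1, 1.5, 2, 2.5, 3, 3.5, and 4 hours", counted from the start of dialysis. Section 4.1 agrees: "A pre-dialyzer plasma sample will be collected at the start of HD".

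Section 9.4 sets the rank of these quantities: "Additional PK endpoints for ESRD participants in Period 2 will include Ca, Cv, AUC(2-6)Ca, and AUC(2-6)Cv". The secondary endpoint for removal by dialysis is CLD,plasma. Section 9.6.3 lists it and summarises it descriptively, and also evaluates removal by the ratio of geometric means before and after dialysis. No formula for CLD,plasma appears; the one clearance formula, in Appendix 10, is for dialysate. Section 9.1 describes Section 9 as a summary and leaves full detail to a separate SAP.

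**The concern.** A trapezoidal area from 2 h needs a concentration at 2 h. Ca has one and Cv does not, so AUC(2-6)Cv cannot be computed as worded without a choice that the text leaves open. Two analysts could report different values from the same samples.

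The stakes rise if CLD,plasma is built from the two areas. The relative error is then largest when extraction is small, which is where a statement that dialysis removes little drug would be most sensitive. A careless choice, such as integrating Cv from 2.5 h against Ca from 2 h, would show removal even where there is none.

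**Working it through.** **Is the mismatch real?** Reproduce the blood volume table first. The schedule gives 1 pre-dialyzer sample at the start plus 8 times × 2 lines = 17 samples. Appendix 8, in the row "Pre- and Post-dialyzer Plasma for MK-6482", also has 17, at 4 mL each = 68 mL. The total is 100 + 7 + 8.5 + 120 + 4 + 68 + 3 + 3 = 313.5 mL, as stated. A post-dialyzer sample at the start would make 18 samples, 72 mL and 317.5 mL, which does not match. So there are 9 Ca values (from about 2 h) and 8 Cv values (from about 2.5 h). The uncovered share is 0.5/4 = 12.5%.

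**How much does the choice matter?** The documents give no extraction value, so what follows is illustration. Assume constant extraction E, Cv = (1 − E) × Ca, and apparent extraction = 1 − AUC(Cv)/AUC(Ca).

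Take flat Ca = 1 and E = 0.10. AUC(Ca) = 4. The observed part of AUC(Cv), 2.5 to 6 h, is 3.5 × 0.9 = 3.15. Two ordinary ways to fill the first half hour:

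- First Cv carried back: 0.5 × 0.9 = 0.45. Then 1 − 3.60/4 = 0.1000.
- Cv at 2 h set equal to Ca at 2 h (no plasma has yet passed the dialyzer): log-down gives 0.5 × (1 − 0.9)/ln(1/0.9) = 0.4746. Then 1 − 3.6246/4 = 0.0939.

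The ratio is 1.07. The same calculation for other assumed cases (one-compartment: absorption 1.2/h, half-life 14 h):

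| Ca profile | E | Carried back | Cv = Ca at 2 h | Ratio |
|---|---|---|---|---|
| Flat | 0.05 | 0.0500 | 0.0469 | 1.07 |
| Flat | 0.10 | 0.1000 | 0.0939 | 1.07 |
| Flat | 0.20 | 0.2000 | 0.1880 | 1.06 |
| Flat | 0.30 | 0.3000 | 0.2824 | 1.06 |
| One-compartment | 0.05 | 0.0486 | 0.0468 | 1.04 |
| One-compartment | 0.10 | 0.0987 | 0.0937 | 1.05 |
| Falling, 6 h half-life | 0.05 | 0.0541 | 0.0462 | 1.17 |
| Falling, 6 h half-life | 0.10 | 0.1039 | 0.0925 | 1.12 |

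The widest ratio, 1.17, can be followed by hand. With k = ln 2/6 = 0.1155/h, AUC(Ca) = (1 − 0.6300)/0.1155 = 3.203. The observed Cv area is 0.95 × (0.9439 − 0.6300)/0.1155 = 2.581, and the first Cv is 0.95 × 0.9439 = 0.8967. Carrying it back adds 0.448; setting Cv equal to Ca at 2 h adds 0.474. Against the true 0.05, the results 0.0541 and 0.0462 are about 8% high and 8% low, and they differ by 0.008 in absolute extraction.

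**What would give large errors?** With flat Ca and E = 0.10:

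- Cv = 0 at 2 h: 0.5 × 0.9/2 = 0.225, so 1 − 3.375/4 = 0.156.
- Cv from 2.5 h against Ca from 2 h: 1 − 3.15/4 = 0.2125; with no removal at all, 1 − 3.5/4 = 0.125.

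The second does not compute the 2 to 6 h area that Section 9.6.3 defines, and nothing in the text suggests the first.

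**Would a matched 2.5 to 6 h window be better?** It is exact if extraction is constant. If extraction in the first half hour is E1 and 0.10 afterwards, the session value is (0.5 × E1 + 3.5 × 0.10)/4. For E1 = 0.05 this is 0.0938 and the matched window, 0.100, is about 7% high; for E1 = 0.15 it is 0.1063 and the matched window is about 6% low. The error is of the same order as the one it would replace, and 12.5% of the session is dropped.

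**The case for a change.** The strongest case for a change is that a named endpoint should be computable from its own schedule, that the convention should be fixed before data are seen, and that one sentence would do it. A wider set of conventions also gives a wider spread: interpolating Cv from zero at dosing gives 0.1112 for flat Ca at E = 0.10, so the range becomes 0.0939 to 0.1112, or 1.18-fold, and 1.32-fold at E = 0.05. And with no formula for CLD,plasma, a reader cannot rule out that the gap reaches the secondary endpoint.

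Part of this stands: the text is silent, and a stated convention would be tidier. The wider spread does not stand. Section 9.6.3 defines Cv as a concentration during dialysis, which starts about 2 h after dosing, so a zero post-dialyzer value at dosing has no meaning. The link to CLD,plasma is possible but not shown. Section 8.3.5 records blood flow, and a clearance built from the eight pairs and that flow would not touch the gap.

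An extra post-dialyzer sample at the start is affordable in principle: 4 mL, against "Up to an additional 50 mL of blood may be drawn for safety and/or PK analyses" in Section 8.11.6 and the matching footnote in Appendix 8. It would gain little, because at that moment no plasma has yet passed the dialyzer.

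Section 4.2.1.1 also speaks of comparing CLD,plasma with controls, who have no dialysis. That is a separate slip of wording; Section 9.4 confines the parameter to ESRD participants in Period 2.

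**Conclusion.** The window and the sampling schedule do not match, but no change to the plan follows. This is missing detail on an additional, per-participant quantity, of the kind Section 9.1 assigns to the separate SAP. That SAP was not supplied and may already settle it. A pharmacokinetic analyst meeting 9 Ca and 8 Cv values would carry the first Cv back, use Ca at the start, or match the windows. No model, confidence interval or decision rests on the result, and the primary AUC0-inf and Cmax comparisons and the before/after-dialysis ratio do not use it.

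The two ordinary fill-ins differ by about 4 to 7% in apparent extraction for flat and one-compartment profiles, and by up to about 17% when Ca falls with a 6 h half-life and extraction is 5%. These figures assume constant extraction, the profiles shown and nominal sampling times. The conclusion would need revisiting only if the separate SAP derived CLD,plasma from these areas with mismatched windows or a zero starting value, and nothing in the documents points to that.
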